### **Supportive Care**

While intrathecal rituximab has been well tolerated in all previously published reports, there are a number of potential toxic effects that will be anticipated. Since hypertension was the dose limiting toxicity in the phase 1 trial, specific aims will be outlined to manage changes in blood pressure around the time of rituximab administration.

Vital signs will be checked every 15 minutes for one hour after each intrathecal administration of rituximab (after one hour, vital signs will return to “routine” unless clinically warranted). For systolic blood pressure greater than 160 mmHg or diastolic blood pressure greater than 100 mmHg, labetalol 20 mg IV will be administered. An alternative agent will be prescribed if the patient’s heart rate is less than 70 beats per minute (e.g. hydralazine, enalaprilat). The management of hypertension can be further individualized if necessary at the discretion of the treating physician. For nausea or vomiting, ondansetron can be considered. If the patient is not over-sedated, a dopamine receptor blocking agent such as promethazine or prochlorperazine can be ordered. These agents will be available on an as needed basis only.

If a patient experiences any chest discomfort, a 12-lead electrocardiogram will be ordered.

For any shortness of breath, bronchodilators such as albuterol will be administered via nebulizer. Supplemental oxygen will be provided to maintain the oxygen saturation greater than 92%, and diagnostic imaging studies (e.g., chest x-ray or chest CT) will be ordered at the discretion of the treating physician or the PI of the study.

Any acute or subacute changes in mental status will warrant magnetic resonance imaging of the brain to rule out leukoencephalopathy.

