#### During Treatment Evaluation

Twice weekly evaluations until two consecutive CSF samples are negative for the presence of blast cells. After the patient's CSF cytology is negative, patients will be evaluated weekly for one month, then every other week thereafter.

- Physical examination, including vital signs, weight and performance status.
- Blood will be drawn for routine tests.
- Concomitant drugs and side effects will be evaluated and recorded.

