### **Analysis method**

Data analysis will be performed using SAS or S-plus, as appropriate. All patients who received at least 1 dose of the agent will be included in the intent-to-treat analysis for efficacy. Demographic and disease characteristics of the patients at registration will be summarized using descriptive statistics such as mean, standard deviation (SD), median and range. Overall response rates will be presented with 95% confidence intervals. The association between response and patient and disease characteristics will be examined by two-sample t-test or Chi-square test.

The data from all patients who received the therapy during the study will be included for safety analysis. Safety data will include laboratory, physical exam, and adverse event reports on study patients. These descriptive summaries will be provided for all patients for each safety parameter by intrathecal rituximab dose #, grade, and relationship to treatment.

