### **Reporting Requirements**

Adverse event reporting will be as per the NCI criteria and the MDACC Leukemia Specific Adverse Event Recording and Reporting Guidelines.

The descriptions and grading scales found in the revised NCI Common Terminology Criteria for Adverse Events (CTCAE) version 4.0 will be utilized for adverse event reporting.  
[\(<http://ctep.cancer.gov/reporting/ctc.html>\).](http://ctep.cancer.gov/reporting/ctc.html)

- Refer to Appendix C for Leukemia-Specific Adverse Event Recording and Reporting Guidelines. Only unexpected AEs will be recorded in the Case Report Form (CRF). The Principal Investigator will sign and date the PDMS Case Report Form toxicity pages per each patient at the completion of each intrathecal rituximab dose #. Following signature, the Case Report Form will be used as source documentation for the adverse events for attribution. PDMS /CORe will be used as the electronic case report form.

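### Adverse events on the CRF are limited to unexpected ones, so non-serious hypertension below grade 3 after an injection has no assured route into the safety summary

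*Protocol*

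**What the plan says.** Supportive Care in the Protocol says of intrathecal rituximab that "there are a number of potential toxic effects that will be anticipated", and goes straight on to blood pressure: "Since hypertension was the dose limiting toxicity in the phase 1 trial, specific aims will be outlined to manage changes in blood pressure". It then sets the schedule: "Vital signs will be checked every 15 minutes for one hour after each intrathecal administration of rituximab". A systolic pressure over 160 mmHg or a diastolic pressure over 100 mmHg calls for IV labetalol, or another agent if the heart rate is low.

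Three sections decide what reaches the safety report:

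- Reporting Requirements: "Only unexpected AEs will be recorded in the Case Report Form (CRF". The same section says that, once signed by the investigator, "the Case Report Form will be used as source documentation for the adverse events for attribution".
- During Treatment Evaluation: "Concomitant drugs and side effects will be evaluated and recorded". It also counts vital signs as part of the physical examination at each visit.
- Analysis method: "Safety data will include laboratory, physical exam, and adverse event reports on study patients", with descriptive summaries "for each safety parameter by intrathecal rituximab dose #, grade, and relationship to treatment".

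The SAP text supplied repeats the statistical section of the Protocol and breaks off within the efficacy monitoring. The Analysis method wording is therefore read from the Protocol.

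**The concern.** Read together, the CRF rule and the Supportive Care text may exclude an effect that the protocol deliberately watches for. If a rise in pressure counts as expected, a grade 1 or 2 event that is not serious need not be entered on the CRF. The CRF is the source for attribution, and the safety summary is broken down by grade and relationship, so an event kept off the CRF may not appear in it.

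Safety is one of the trial's two stated objectives. The drug is given here by lumbar puncture at 10 and 25 mg, whereas most patients in the earlier phase 1 study received it through an Ommaya reservoir. Lower-grade pressure data by this route are worth reporting, and the readings are already being taken. At stake is the completeness of a descriptive table; decisions made during the trial do not depend on it.

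**Working it through.** The plan gives no figure on this point to reproduce. The check follows one event, a non-serious rise below grade 3 in the hour after an injection, through each capture route in the Protocol.

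1. **Dose-limiting toxicity (Dose Escalation Procedures).** Requires CTCAE grade 3 or 4. Does not capture the event.
2. **Phase II toxicity monitoring.** Counts non-hematological grade 3 or higher. Does not capture the event. This monitoring is sound in itself: with a Beta(0.6, 1.4) prior and the rule Pr(P_E > 0.3 | data) > 0.9, the stated boundaries 4/6, 5/8, 6/10, 7/13, 8/15, 9/18 and 10/21 are reproduced. With looks from patient 6 to patient 21, the stopping probabilities are 0.050, 0.228, 0.539 and 0.824, against the stated 0.05, 0.22, 0.54 and 0.82.
3. **Serious adverse event reporting.** Serious events only. Does not capture the event.
4. **CRF adverse-event entries (Reporting Requirements).** Captured only if judged unexpected. Supportive Care points the other way, but no section supplied defines expectedness.
5. **Side effects at each evaluation.** No limit by grade or expectedness, but the place of recording is not stated. Not assured.
6. **Physical examination.** Visit vital signs are safety data. Nothing says that the post-injection series belongs to them. Not assured.
7. **Concomitant medication (entered in the electronic CRF).** A treated rise leaves a drug entry without the pressure reached. A rise to no more than 160 systolic and 100 diastolic does not meet the treatment trigger and may leave no entry.
8. **Appendix C.** Cited for adverse-event capture and source documentation, but not in the text reviewed. It may close the gap.

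The CTCAE scale is not reproduced, so the documents do not show whether a reading above 160/100 is grade 3. If it is, and is graded so, routes 1 and 2 already reach it, subject for route 1 to clinical significance and attribution.

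The volume of data already taken can be counted. Inputs are the vital-sign interval (Supportive Care), the injection schedule (Selection of Patients) and the removal rule (Criteria for Removal from Study). It is assumed that CSF is sampled at each puncture.

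- Readings per injection: 60 / 15 = 4.
- Removed as resistant after four injections: 4 × 4 = 16 readings.
- Full course with two twice-weekly injections: 2 + 4 weekly + 4 every other week = 10 injections; 10 × 4 = 40 readings.
- First negative sample only after the fourth injection, second still needed: at least 5 + 4 + 4 = 13 injections; 13 × 4 = 52 readings or more, with no stated ceiling.

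One maximum systolic and diastolic pair per injection means 4, 10, and 13 or more pairs. The ratio is 4/16 = 10/40 = 13/52 = 1/4 of the readings.

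**The case against.** The strongest reply is that the gap depends on two things the text does not settle. First, to anticipate an effect in supportive care is not to classify it as expected for reporting. The background on systemic rituximab lists hypotension, not hypertension, among the main infusion effects. Judged against that list, a rise would be unexpected and would go on the CRF. Second, Appendix C covers exactly this subject and cannot be read here. Both points stand. They limit the finding to a route that is not assured; they do not show that the route exists.

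It can also be said that the investigator signs CRF toxicity pages after each injection, and that the adverse event reports named in Analysis method are not confined to CRF entries. The signed pages fall under the same unexpected-only rule, so they do not cure the problem. The second remark is fair: the link from CRF to summary is an inference from the CRF's role as source for attribution.

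Little is left uncaptured. Readings above 160/100 normally lead to a recorded drug, and grade 3 or higher and serious events are covered. In the earlier study hypertension was dose-limiting at 50 mg, twice the highest dose here, and very little toxicity was noted at 25 mg. This stands, and it is why the priority is low.

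**Conclusion.** The point holds in a narrow form. As written, the plan does not assure that non-serious hypertension below grade 3 reaches the summary by injection number, grade and relationship, and it does not name the post-injection vital signs among the safety data. It is a low-priority, inexpensive improvement.

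The documents give no rate of post-injection rises, so the number of events lost cannot be estimated. It is zero if Appendix C, or the side-effect record made at each evaluation, feeds the CRF. The conclusion assumes that a pressure rise would be treated as expected.

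A reader might infer more, without support from the documents:

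- *That post-injection blood pressure is never entered or summarised.* The safety-data list is not closed, visit vital signs are within it, and treated rises leave a medication entry.
- *That hypertension escapes safety monitoring.* Clinically significant grade 3 or 4 events not attributed to other causes count as dose-limiting, and grade 3 or higher counts in phase II monitoring. No stopping rule, endpoint or patient management is affected.
- *That the appendix is a missing part of the plan.* It was only absent from the text reviewed.

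**What to change.** (a) In Reporting Requirements, add one sentence: treatment-emergent hypertension of every grade is entered on the CRF with grade and attribution, whether or not it is expected. If Appendix C already requires this, a cross-reference is enough.

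(b) In Analysis method, name post-injection vital signs as safety data and add a summary by dose level of the last available pre-injection pressure, the maximum post-injection systolic and diastolic pressures, and the number of patients with a reading above 160 systolic or 100 diastolic or given an IV antihypertensive. The denominator is patients with at least one post-injection reading. The pre-injection value is needed because a maximum alone cannot separate a rise from long-standing hypertension. Label the table descriptive: with no control arm, and with premedication and systemic chemotherapy allowed, it does not estimate a drug effect.

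The cost is a few sentences, some lower-grade CRF entries, one extra table, and about one pair of maximum pressures per injection (4, 10, or 13 or more pairs per patient in the three cases above). If visit vital signs are not already entered, the pre-injection value adds a second pair, giving 8, 20, or 26 or more. The post-injection readings are already scheduled, so no new visit, procedure or timing rule is needed.

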### **Patient Data Confidentiality**

Patient data will be collected, analyzed, distributed and managed in accordance with the M. D. Anderson Confidentiality Policy. Only the PI and research staff will have access to the data. The data will be stored on a password protected computer in a locked office.

### **Reporting Requirements**

Adverse event reporting will be as per the NCI criteria and the MDACC Leukemia Specific Adverse Event Recording and Reporting Guidelines.

The descriptions and grading scales found in the revised NCI Common Terminology Criteria for Adverse Events (CTCAE) version 4.0 will be utilized for adverse event reporting.  
[\(<http://ctep.cancer.gov/reporting/ctc.html>\).](http://ctep.cancer.gov/reporting/ctc.html)

- Refer to Appendix C for Leukemia-Specific Adverse Event Recording and Reporting Guidelines. Only unexpected AEs will be recorded in the Case Report Form (CRF). The Principal Investigator will sign and date the PDMS Case Report Form toxicity pages per each patient at the completion of each intrathecal rituximab dose #. Following signature, the Case Report Form will be used as source documentation for the adverse events for attribution. PDMS /CORe will be used as the electronic case report form.

### **Serious Adverse Event Reporting (SAE) for M. D. Anderson-Sponsored IND Protocols**

An adverse event or suspected adverse reaction is considered “serious” if, in the view of either the investigator or the sponsor, it results in any of the following outcomes:

- Death
- A life-threatening adverse drug experience – any adverse experience that places the patient, in the view of the initial reporter, at immediate risk of death from the adverse experience as it occurred. It does not include an adverse experience that, had it occurred in a more severe form, might have caused death.
- Inpatient hospitalization or prolongation of existing hospitalization
- A persistent or significant incapacity or substantial disruption of the ability to conduct normal life functions.
- A congenital anomaly/birth defect.

Important medical events that may not result in death, be life-threatening, or require hospitalization may be considered a serious adverse drug experience when, based upon appropriate medical judgment, they may jeopardize the patient or subject and may require medical or surgical intervention to prevent one of the outcomes listed in this definition. Examples of such medical events include allergic bronchospasm requiring intensive treatment in an emergency room or at home, blood dyscrasias or convulsions that do not result in inpatient hospitalization, or the development of drug dependency or drug abuse (21 CFR 312.32).

- Important medical events as defined above, may also be considered serious adverse events. Any important medical event can and should be reported as an SAE if deemed appropriate by the Principal Investigator or the IND Sponsor, IND Office.
- All events occurring during the conduct of a protocol and meeting the definition of a SAE must be reported to the IRB in accordance with the timeframes and procedures outlined in “The University of Texas M. D. Anderson Cancer Center Institutional Review Board Policy for Investigators on Reporting Unanticipated Adverse Events for Drugs and Devices”. Unless stated otherwise in the protocol, all SAEs, expected or unexpected, must be reported to the IND Office, regardless of attribution (within 5 working days of knowledge of the event).
- **All life-threatening or fatal events**, that are unexpected, and related to the study drug, must have a written report submitted within **24 hours** (next working day) of knowledge of the event to the Safety Project Manager in the IND Office.
- Unless otherwise noted, the electronic SAE application (eSAE) will be utilized for safety reporting to the IND Office and MDACC IRB.
- Serious adverse events will be captured from the time of the first protocol-specific intervention, until 30 days after the last dose of drug, unless the participant withdraws consent. Serious adverse events must be followed until clinical recovery is complete and laboratory tests have returned to baseline, progression of the event has stabilized, or there has been acceptable resolution of the event.
- Additionally, any serious adverse events that occur after the 30 day time period that are related to the study treatment must be reported to the IND Office. This may include the development of a secondary malignancy.

(Please see Appendix C regarding data capturing of adverse events and adverse events source documentation.)

**Reporting to FDA:**

- Serious adverse events will be forwarded to FDA by the IND Sponsor (Safety Project Manager IND Office) according to 21 CFR 312.32.

**It is the responsibility of the PI and the research team to ensure serious adverse events are reported according to the Code of Federal Regulations, Good Clinical Practices, the protocol guidelines, the sponsor's guidelines, and Institutional Review Board policy.**

Unacceptable severe (grade 3-4) toxicity that is possibly related to the study drug and persists despite dose optimization and optimal management of toxicity.

Patient choice

Failure to comply with study schedule

Statistical Considerations

The primary outcome of the study will be response rate. Time to recurrence of CNS leukemia and overall survival will be secondary outcomes. Time to recurrence and survival will be considered from the date of CNS relapse diagnosis.

There is no well-defined metric to measure response to treatment in patients with peripheral nerve involvement only. Clinical and radiologic response will be recorded and it is expected that few to no patients with only peripheral nerve involvement will actually be involved and therefore the statistical analysis will not be affected.

A maximum of 25 patients will enrolled in this phase I/II study, with about 12 patients/year.

Phase I

First, phase I study is performed to assess the safety of two dose levels for rituximab: 10mg and 25mg. These two dose levels have been previously in a small series (12). A 3+3 design will be used to for dose escalation. Detailed dose escalation rules are described in the following section. A maximum of 12 patients will enroll in the phase I study.

Dose Escalation Procedures

The dose of treatment agent will be escalated in successive cohorts of patients. The starting dose is at dose 0 as shown in table 1. Enroll 3 patients at the dose level and proceed to the next higher dose level with a cohort of 3 patients until at least 1 patient experiences a dose-limiting toxicity (DLT).

DLT is defined as a clinically significant adverse event or abnormal laboratory value assessed as unrelated to disease progression, intercurrent illness, or concomitant medications and meeting the NCI common terminology criteria that are CTCAE Grade 3 or 4.

An adverse event must be clinically significant to define DLT e.g. alopecia, study drug-related fever, electrolyte abnormalities (including K, Na, Cl, HCO3, Mg, Ca) that are < Grade 3 will not define the DLT. Drug-related Grade 3-4 nausea and vomiting not controlled with adequate therapy will be considered DLTs.

If only 1 of 3 patients experiences a DLT at a given dose level, enter 3 additional patients at the current dose level. If only 1 of 6 patients experiences a DLT at a given dose level, proceed to the next higher dose level with a cohort of 3 patients. If at least 2 of 3 or 2 of up to 6 patients experience a DLT at a

given dose level, then the MTD has been exceeded (stopping dose). Once the MTD has been exceeded, treat another 3 patients at the previous dose level if there were only 3 patients treated at that dose level. The MTD is defined as the highest dose level in which 6 patients were treated with at most 1 experiencing a DLT during the 1st cycle.

In summary, our dose escalation plan is as follows: during phase I, the starting dose is 10 mg and dose escalation will follow a 3 + 3 design. After three patients have received 10 mg, if there is no DLT, the next cohort of three patients will receive 25 mg. If there is one DLT in the initial three patients, an additional three patients will be treated at 10 mg. If 2/6 patients experience a DLT at 10 mg, the study will be closed. If less than or equal to 1/6 at 10 mg experience a DLT, we will enroll the next three patients at 25 mg. The maximum dose on this protocol is 25 mg, thus, no further dose escalation will occur. If 1/3 patients at 25 mg experience a DLT, we will enroll three additional patients at 25 mg. If 2/6 experience a DLT, all subsequent patients will receive 10 mg, and that will be the final dose. If less than or equal to 1/6 experience a DLT at 25 mg, the remainder of the patients enrolled will receive 25 mg. If 2/3 or 2/6 patients experience a DLT at the 10 mg dose, the study will be terminated.

Table 1. Dose levels of rituximab

Dose level	rituximab
0 (starting dose)	10 mg
1	25 mg

Phase II

Phase II part is a single arm study using the dosage level recommended from phase I. The patients treated at the MTD in phase I will be included in phase II part, and the sample size for phase II can be up to 22. The trial will be continuously monitored for efficacy and toxicity (non-hematological ≥grade 3). The method of Thall, Simon, and Estey will be used to perform interim efficacy and safety monitoring (15).

Efficacy

The primary endpoint is the response defined as the CNS is without evidence of blast cells after four lumbar punctures with rituximab. The historical data suggested the response rate by chemotherapy (methotrexate and/or cytarabine) is about 10%. The targeted improved overall response rate is 25%, The trial will be continuously monitored. The study will be stopped early if the data suggest that:

$$Pr(\pi > 0.1 | data) < 0.05$$

Here π is the response rate. That is, if at any time during the study we determine that there is a less than 5% chance that the response rate is greater than 10%, we will terminate the study. The response
